16.3. OTHER EFFICACY

The other efficacy analyses will be performed for the mITT population.

- Moderate/severe COPD exacerbation frequency of patients using full study length, period truncated at week 24 visit and for patients in 48-week stratum (this individual study and pooled with data from study RPL554-CO-302).
- Time to first moderate/severe COPD exacerbation of patients using full study length, period truncated at week 24 visit and for patients in 48-week stratum (this individual study and pooled with data from study RPL554-CO-302).
- Study withdrawal before scheduled visit at 24 and 48 weeks.
- Change from baseline to post-baseline EQ-5D-5L using Health index and VAS score at Week 12
- HRU over 24 and 48 weeks
- Change from baseline FEV₁ to average FEV₁ AUC_{6-12h} at Week 12
- E-RS responder analysis
- Morning trough FEV₁ responder analysis
- Change from baseline SGRQ score by domain: symptoms, activity, impacts
- Change from baseline E-RS score by domain: breathlessness, cough and sputum, chest symptoms

16.3.1. OTHER EFFICACY VARIABLES & DERIVATIONS

16.3.1.1. COPD exacerbation

COPD exacerbations are collected on the “COPD Exacerbation” page of the eCRF and severity will be derived separately using data collected in the eCRF and as per the criteria specified in Section 11.6.1. of the study protocol.

Site must enter at least 2 major symptoms, or one major symptom and one minor symptom AND meet the severity criteria below, considered as a moderate/severe exacerbation of COPD.

The severity of the COPD exacerbation will be calculated as per the following:

Moderate: Worsening symptoms of COPD requiring a minimum of three days of treatment with oral/systemic corticosteroids and/ or antibiotics.

Severe: Worsening symptoms of COPD requiring in-patient hospitalization.

[REDACTED]

16.3.1.2. Time to study withdrawal

Time to study withdrawal will be derived as follows:

- For patients who completed the study: Use the day of final week 24 or week 48 clinic visit, depending on which stratum the patient is randomized into
- For patients who did not complete the study but not lost to follow-up: If available, use the end of study date. If not available, use the last site contact out of any assessment (excluding eDiary).
- For patients who are lost to follow-up: the censoring date will be their last reported site contact.

16.3.1.3. EQ-5D-5L

Quality of Life (QoL) was assessed using the EQ-5D-5L questionnaire. This questionnaire consists of 5 domains: mobility, self-care, usual activities, pain/discomfort and anxiety/depression with 5 possible responses from 1 (no problem) to 5 (unable). The sixth item, referred to as a visual analogue scale (VAS) score, is an index score to self-rate health from 0 (worst) to 100 (best). Each of the 5 domains will be summed through weighing system into a health index. The health index and VAS score will be analysed and listed and 5 domains will be only listed. It is not possible to have missing items in the questionnaire, as the data are collected in an electronic tablet which doesn't allow patients to skip between items. The weighting system is described in Appendix 6 of the SAP.

16.3.1.4. HRU

HRU is measured by the following events: unscheduled visits to a physician office, visits to urgent care, visits to emergency department and hospitalizations for any cause and/or related to COPD and visits/contact due to COPD exacerbation. These will be recorded on the Log Form and "COPD Exacerbation" pages of the eCRF, respectively.

16.3.1.5. Patient Perception Survey

At the follow-up contact each patient will fill in a survey on their perception of what drug they were on. Data recorded on "Patient Perception Survey" page of the eCRF will be listed and summarized by treatment group for the following categories:

- Patients who correctly guessed their drug
- Patients who incorrectly guessed their drug
- Patients who were unsure of their drug

16.3.1.6. FEV₁ AUC_{6-12h}

Average FEV₁ AUC_{6-12h} is calculated as described in Section 16.1.1.1 of the SAP.

[REDACTED]

16.3.1.7. E-RS total score responder

E-RS total score responder is defined as a decrease from baseline in the week mean total of E-RS score of greater than or equal to 2.

16.3.1.8. Morning trough FEV₁ responder

Morning trough FEV₁ responder is defined as an increase from baseline in the Morning trough FEV₁ greater than or equal to 100 mL.

16.3.1.9. SGRQ domains

SGRQ questionnaire is composed of three domains: symptoms, activity, and impacts as described in Section 16.2.1.2.2 of the SAP. Subdomain scores are calculated as follows:

- Symptoms score = sum of items 1 to 8 of SGRQ questionnaire
- Activity score = sum of items 11 and 15 of SGRQ questionnaire
- Impacts score = sum of items 9, 10, 12, 13, 14, 16 and 17 of SGRQ questionnaire

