16.2.1.2.2. SGRQ

St. George's Respiratory Questionnaire (SGRQ) is a questionnaire consisting of 17 questions, split into two parts. Part 1 consists of the first 8 questions and is related to the Symptoms subdomain. The remaining 9 questions are in Part 2, which are related to the Activity and Impacts subdomains. Each possible answer to each question has a weight assigned described in the Appendix 5.

Note that question 6 (How long did the worst respiratory attack last?) has an additional instruction, “Go to Question 7 if you did not have a severe attack”. If question 6 has not been answered, it will be assigned a weight of zero.

Calculating the score

Subdomains:

- Symptoms – items 1 to 8
- Activity – items 11 and 15
- Impacts – items 9, 10, 12, 13, 14, 16 and 17

The score for each component is calculated separately by dividing the summed weights by the maximum possible weight for that component and expressing the result as a percentage. It is not possible to have missing items in the questionnaire, as the data are collected in an electronic tablet which doesn’t allow patients to skip between items.

$$\text{Component score} = 100 * \frac{\text{Sum of weights from all positive items in that component}}{\text{Sum of maximum weights for all items in that component}}$$

The total score is calculated similarly

$$\text{Total score} = 100 * \frac{\text{Sum of weights from all positive items in that questionnaire}}{\text{Sum of maximum weights for all items in that questionnaire}}$$

The higher the score the more severe impact of COPD on patient’s life.

Sum of maximum possible weights for each component and Total:

Symptoms = 662.5

Activity = 1209.1

Impacts = 2117.8

Total = 3989.4

16.2.1.2.3. **BDI/ TDI**

Baseline Dyspnea Index (BDI) and Translational Dyspnea (TDI) are questionnaires that focus on three subdomains: Functional impairment, Magnitude of task and Magnitude of effort. BDI is collected at baseline (Day 1) and TDI is collected post-baseline (Weeks 6, 12 and 24).

Subdomain score is calculated as the sum from the related questions. Total score is calculated as the sum of the subdomain scores.

If at least one of the scores is missing, then total score is set to missing.

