APPENDIX 6. EQ-5D-5L WEIGHTS

To account for this study collecting data in multiple countries, different EQ-5D-5L weights will be used depending on the country, as presented in Table 5.

Table 5: EQ-5D-5L geographical region categorisation

Countries	Version used
Eastern Europe: Bulgaria, Czech Republic, Greece, Hungary, Poland, Romania, Russian Federation, Slovakia	Poland (EQ-VT v2.0)
Western Europe: Germany, United Kingdom	England (EQ-VT v1.0)\
North America: US	US (EQ-VT v2.0)
Asia: Republic of Korea	South Korea (EQ-VT v2.0)

Data collected from questionnaire will be numbered, as presented in Table 6.

Table 6: EQ-5D-5L data collection

Variable name	Mobility	Self-care	Usual Activities	Pain/Discomfort	Anxiety/Depression	Health score	VAS
Variable score range	1-5	1-5	1-5	1-5	1-5	5-digit code for EQ-5D-5L	0-100
Data row example	2	3	1	1	1	23111	83

The health score is a combination of the scores for the 5 questions (mobility, self-care, usual activities, pain/discomfort and anxiety/depression) in the order they are collected, as shown in the data row example in Table 6.

POLAND

The health index is calculated by first summing all weights related to the scores from the questionnaire and subtracting it from 1, i.e. for data row example in Table 6 the health index would be 0.928. Weights related to each score are presented in Table 7.

Table 7: Weights

Variable	Score	Weights
Mobility	1	0
	2	0.025
	3	0.034
	4	0.126
	5	0.314
Self-care	1	0
	2	0.031
	3	0.047
	4	0.111
	5	0.264
Usual Activities	1	0
	2	0.023
	3	0.040
	4	0.097
	5	0.205
Pain/discomfort	1	0
	2	0.030
	3	0.050
	4	0.261
	5	0.575
Anxiety/ depression	1	0

[REDACTED]

[REDACTED]

[REDACTED]

[REDACTED]

[REDACTED]

	2	0.018
	3	0.029
	4	0.108
	5	0.232

ENGLAND

The health index is calculated by first summing all weights related to the scores from the questionnaire and subtracting it from 1, i.e. for data row example in Table 6 the health index would be 0.879. Weights related to each score are presented in Table 8.

Table 8: Weights

Variable	Score	Weights
Mobility	1	0
	2	0.058
	3	0.076
	4	0.207
	5	0.274
Self-care	1	0
	2	0.050
	3	0.080
	4	0.164
	5	0.203
Usual Activities	1	0
	2	0.050
	3	0.063

[REDACTED]

[REDACTED]

[REDACTED]

[REDACTED]

[REDACTED]

[REDACTED]

[REDACTED]

[REDACTED]

[REDACTED]

[REDACTED]

	4	0.162
	5	0.184
Pain/discomfort	1	0
	2	0.063
	3	0.084
	4	0.276
	5	0.335
Anxiety/ depression	1	0
	2	0.078
	3	0.104
	4	0.285
	5	0.289

US

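### SAP 16.3.1.9 scores the SGRQ domains as plain item sums, while SAP 16.2.1.2.2 scores the same domains as 0–100 percentages

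*SAP*

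**What the plan says.** SAP 16.2.1.2.2 assigns a weight (Appendix 5) to each answer, allocates items to Symptoms, Activity and Impacts, and scores each component by "dividing the summed weights by the maximum possible weight for that component and expressing the result as a percentage". It then lists the divisors, starting with "Symptoms = 662.5" and followed by 1209.1 for Activity, 2117.8 for Impacts and 3989.4 for the total.

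SAP 16.3.1.9 covers the same three domains. It points back to 16.2.1.2.2 when it describes how the questionnaire is made up, and then introduces a calculation of its own. The rule given there for the first domain is "Symptoms score = sum of items 1 to 8 of SGRQ questionnaire". Activity and Impacts are handled in the same way, as plain sums over their two and seven items respectively.

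There is no divisor and no multiplication by 100. Section 16.3.3 sends the domain scores to the change-from-baseline ANCOVA, and 16.3.2 sends their missing values to the continuous multiple-imputation method. Neither names a scoring rule. Section 3.3, which announces the domain analysis as an addition to the protocol, gives score ranges for the E-RS domains but none for the SGRQ domains.

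Appendix 6 separately gives a worked EQ-5D-5L index for health state 23111 under each of four country value sets. The England value is printed as 0.879.

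**The concern.** One analysed variable should have one derivation. The item-to-domain allocation is the same in both sections, so the conflict lies only in the arithmetic. The section that a programmer would open for the domain analysis is the one without the divisor.

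The likely origin is the adjacent E-RS text. Section 16.3.1.10 uses the same sum wording for the E-RS domains, and there it is right, because 16.2.1.2.1 defines those subdomains as sums of raw scores (0–17, 0–11 and 0–12). The SGRQ is not scored that way in this SAP.

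If the sums were programmed, the domain tables would show LS means, differences and intervals in units of raw weight, with a different unit for each domain. A reader could not set one domain beside another or beside the 0–100 total score. The 4-unit improvement used for the total-score responder would offer no guide to their size.

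The England example raises a smaller issue of the same kind. Someone validating correct EQ-5D-5L code for the German and UK patients against it would see a mismatch that is not real.

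**Working it through.** **1. Reproduce the SAP's divisors from Appendix 5.** For single-choice items (1–10 and 17) take the largest answer weight. For multi-statement items (11–16) add all statement weights. The statement on being unable to move far from bed or chair (94.0) is counted in item 16; the extracted table shows it beneath the item 17 heading.

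- Symptoms (items 1–8): 80.6 + 76.8 + 87.2 + 86.2 + 86.7 + 89.7 + 93.3 + 62.0 = 662.5
- Activity (items 11 and 15): 558.3 + 650.8 = 1209.1
- Impacts (items 9, 10, 12, 13, 14, 16, 17): 83.2 + 88.9 + 493.4 + 663.4 + 293.5 + 398.7 + 96.7 = 2117.8
- Total: 662.5 + 1209.1 + 2117.8 = 3989.4

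All four agree with 16.2.1.2.2.

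**2. Ratio of the two rules.** Let S be a patient's summed weights in a domain and M the domain maximum. Section 16.2.1.2.2 gives 100 × S / M and 16.3.1.9 gives S. The ratio is S ÷ (100 × S / M) = M / 100, the same for every patient in that domain.

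| Domain | M | Range, 16.2.1.2.2 | Range, 16.3.1.9 | Ratio M/100 | 4 points on the 0–100 scale become 4 × M/100 |
|---|---|---|---|---|---|
| Symptoms | 662.5 | 0–100 | 0–662.5 | 6.625 | 26.5 |
| Activity | 1209.1 | 0–100 | 0–1209.1 | 12.091 | 48.4 |
| Impacts | 2117.8 | 0–100 | 0–2117.8 | 21.178 | 84.7 |

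**3. Effect on the ANCOVA.** Outcome and baseline are multiplied by the same constant, so the estimate and its standard error scale together and their ratio does not move. A least-squares check on simulated data (500 vs 300 patients, adjusting for baseline) confirmed this. On the original scale the estimate was −1.867 with SE 1.062. Multiplied by 6.625 it was −12.371 with SE 7.036. In both cases t = −1.758 and p = 0.0791, and the other two factors gave the same t and p. The continuous imputation method has no range limits, so rescaling leaves it unaffected apart from Monte Carlo error.

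**4. EQ-5D-5L examples, state 23111.** The rule is 1 minus the sum of the weights. Only mobility level 2 and self-care level 3 contribute, since level 1 has weight 0.

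| Value set | Calculation | Result | SAP |
|---|---|---|---|
| Poland | 1 − 0.025 − 0.047 | 0.928 | 0.928 |
| England | 1 − 0.058 − 0.080 | 0.862 | 0.879 |
| US | 1 − 0.096 − 0.107 | 0.797 | 0.797 |
| South Korea | 1 − 0.063 − 0.062 | 0.875 | 0.875 |

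The England example is too high by 0.879 − 0.862 = 0.017. The printed value equals 1 − 0.058 − 0.063, and 0.063 is the Table 8 weight for usual activities at level 3, which suggests that it was read from the wrong row.

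**The case against.** The strongest reply is that 16.3.1.9 refers to 16.2.1.2.2, where the formula and the three divisors are set out, and that the component divisors have no other use in the SAP. On that reading the three lines merely restate which items belong to which domain, and a careful programmer would use the percentages. This makes the raw-sum outcome less likely, but it does not remove the conflict. The reference is attached to the composition of the questionnaire, and the next sentence introduces a calculation of its own.

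Other points stand as limits on the size of the problem:

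- 16.3.1.9 does not mention weights. The ratios hold if an item's value is its Appendix 5 weight, the only SGRQ item value that the SAP defines. If response codes were summed instead, the ratio would not be constant and could not be computed from the documents.
- Within a domain the discrepancy is a change of units. It cannot create or remove a significant result.
- The SAP plans no domain-level responder analysis and no formal comparison between domains, so what suffers is the reading of the estimates, not a planned test.
- The EQ-5D-5L error is clerical and concerns a different instrument. The operative rule and Table 8 are clear without the example.

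**Conclusion.** The point holds, as a minor one. The SAP contains two incompatible calculations for the SGRQ domain scores, and the one in the domain section conflicts with the SAP's own component scoring. If it were followed, reported domain estimates, standard deviations and confidence limits would be 6.6, 12.1 and 21.2 times their values on the percentage scale for Symptoms, Activity and Impacts, given that items carry their Appendix 5 weights.

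The reach is limited to the domain analysis listed under other efficacy in SAP 16.3, outside the testing hierarchy of SAP 7.4. The SGRQ total score and the total-score responder analysis use the 0–100 total and are untouched. The England example is a separate slip of 0.017 in an illustration and changes no planned result if the code follows Table 8.

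**What to change.** In SAP 16.3.1.9, replace the three sum lines with the component formula of 16.2.1.2.2: 100 × summed weights ÷ 662.5 for Symptoms, ÷ 1209.1 for Activity and ÷ 2117.8 for Impacts. Leave the E-RS sums in 16.3.1.10 as they are. In Appendix 6, change the England example from 0.879 to 0.862.

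The cost is a few lines of SAP text, with no effect on data collection or timelines.

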16.3.1.10. E-RS domains

E-RS EXACT-PRO questionnaire is composed of three domains: breathlessness, cough and sputum, and chest symptoms as described in Section 16.2.1.2.1 of the SAP. Scores are calculated as follows:

- Breathlessness score = sum of items 7 to 11 of E-RS questionnaire
- Cough and sputum score = sum of items 2 to 4 of E-RS questionnaire
- Chest symptoms score = sum of items 1, 5 and 6 of E-RS questionnaire

16.3.2. MISSING DATA METHODS FOR OTHER EFFICACY VARIABLES

For EQ-5D-5L missing data will be imputed using imputation described in Section 16.2.2.13 of the SAP (MI range method) and FEV₁ AUC_{6-12h} missing data, E-RS and SGRQ domain missing data will be imputed using imputation described in Section 16.2.2.1 of the SAP (MI continuous method). Morning trough FEV₁ responder missing data will be handled as described in Section **Error! Reference source not found.** of the SAP (MI range method). E-RS total score responder missing data will be imputed similar to the SGRQ total score responder analysis as described in Section 16.2.2.32 of the SAP (MI range method).

16.3.3. ANALYSIS OF OTHER EFFICACY VARIABLES

Change from baseline to average FEV₁ AUC_{6-12h} will be analyzed using ANCOVA approach and missing data will be imputed using imputation, as described in Sections 16.1.3 and 16.2.2.1 of

[REDACTED]

the SAP, respectively.

Model assumptions will be tested and solved, if failed, as per Section 16.1.3 of the SAP.

The rate of and time to first moderate/severe COPD exacerbations will be analyzed in three cut-off rules:

- All patients (patients in 24-week and 48-week strata combined) using full study length
- Period truncated at Week 24 visit (patients in 24-week and 48-week strata combined)
- Patients in 48-week stratum using full study length

For each of the three rules above, the number of patients who experienced COPD exacerbation will be presented by week, follow-up and overall. Similarly, the duration of COPD exacerbation (in days) and the time in study will be calculated based on the cut-off rules.

Weekly percentage of patients who experienced COPD exacerbation will be based on the treatment population being analyzed. For All patients and Period truncated at Week 24 visit, the percentage will have denominator of mITT population. Analysis using 48-week stratum only will have mITT patients in this stratum as denominator.

For each cut-off rule, the number of moderate/severe COPD exacerbations will be analyzed using a negative binomial model adjusting for treatment, region, actual background medication strata and actual smoking strata, as well as using log study time (years) as an offset. If the model does not converge, the covariate that causes the issue will be removed from the model. The number of patients who experienced exacerbations and the number of exacerbations will also be presented using the data used to analyze negative binomial model.

The logic for time in study used as offset or for censoring purpose is as follows:

- For 24-week completers, use the day of final week 24 clinic visit. For 48-week completers, use the day of the final week 48 clinic visit.
- For non-completers who are not lost to follow-up, use the end of study date, which is assumed to be their end of study visit.
 - If no end of study date, use the last site contact out of any assessment (excluding eDiary)
- For subjects who are lost to follow-up, the censoring date will be at their last reported site contact.

Moderate/severe exacerbations occurring after the day used as offset will not be considered in the analysis. The treatment difference from the negative binomial model will be expressed as an

[REDACTED]

annualized risk ratio. The data will also be summarized by treatment group over duration of the study period. Only moderate/severe COPD exacerbations meeting the protocol-specified criteria will be presented in the listing.

Time to study medication withdrawal or study withdrawal will be presented per stratum and by the following subgroups: patients who withdrew from study medication/study before Week 24 visit and patients who withdrew from study medication/study before Week 48 visit for 48-week stratum.

Time to first moderate/severe COPD exacerbation during the study period will be presented for all patients using full study length, all patients using data truncated at week 24 visit, and patients in 48-week stratum. The primary analysis will include log-rank test stratified by region, actual background medication strata and actual smoking strata. Summary of number of patients with events and number of patients censored will be presented. Outcome will be visualized using a Kaplan-Meier plot.

The health index and VAS score for EQ-5D-5L questionnaire will be analyzed using ANCOVA approach, as described in Section 16.1.3 of the SAP, with data imputation described in Section 16.2.2.3 of the SAP.

HRU over a period truncated up to Week 24 visit for all patients (24-week and 48-week strata combined) and for 48-week stratum only will be summarized for each event and for overall count. HRU during follow-up period will not be presented.

- Sensitivity analysis or subgroup analysis may be considered following results of the patient perception survey. The survey will be summarized to investigate if there are any signs of breaching of the blind related to the appearance of study medication.
- Proportion of E-RS total score responders will be analyzed by means of a logistic regression model with fixed effects for treatment, region, actual background medication strata and actual smoking strata at baseline and baseline E-RS total score as covariate. Missing data will be imputed as described in Section 16.2.2.3 (range method).
- Proportion of responders, with an improvement from baseline in Morning trough FEV₁ of 100 mL or more will be analyzed using a logistic regression model with fixed effects for treatment, region, actual background medication strata and actual smoking strata at baseline and baseline Morning trough FEV₁ as covariate. Missing data will be imputed as described in Section 16.2.2.3 (range method).

[Redacted content]

- Change from baseline SGRQ scores and E-RS scores will be analyzed by domain using ANCOVA approach as described in Section 16.2.3.1 of the SAP.

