6.4. WINDOWING CONVENTIONS

Each visit (except for Day 1 visit) will have a ± 10 days window. No visit windowing will be applied during the analysis to the data that is only collected at scheduled site visits for patients that have completed the study, and therefore the data will be presented as per the visit reported in the database.

For endpoints based on 12 hour spirometry data, (FEV1 AUC0-12h, FEV1 evening trough and FEV1AUC6-12h), data collected at visits with 12 hour spirometries will be included in the analysis regardless of the timepoint it was generated. Hence, no windowing convention applied to these endpoints.

For the patients that discontinued from the study, the End of Study (EOS) visit will be windowed to the corresponding visit, based on the study day, for questionnaire, spirometry and rescue medication data. The EOS visit can only be windowed to a visit that is missing or has a missing result. The rules for the windowing are described below.

[REDACTED]	[REDACTED]	[REDACTED]	[REDACTED]
[REDACTED]	[REDACTED]	[REDACTED]	[REDACTED]
[REDACTED]	[REDACTED]	[REDACTED]	[REDACTED]
[REDACTED]	[REDACTED]	[REDACTED]	[REDACTED]

- For spirometry raw data and derived data that happens at every visit, windowing will be done as per the corresponding visits.
 - Day 1 = Day 1
 - Week 6 = after Day 1 and up to and including Day 53
 - Week 12 = after Day 53 and up to and including Day 95
 - Week 24= after Day 95 and up to and including Day 179
- For spirometry derived data that only happen at certain visits, windowing will be done for the corresponding visits.
 - For morning trough:
 - Week 6 = after Day 1 and up to and including Day 53
 - Week 12 = after Day 53 and up to and including Day 95
 - Week 24= after Day 95 and up to and including Day 179
 -
- For rescue medication data, E-RS/EXACT-PRO, e-diary data and COPD exacerbation, windowing will be done as per the corresponding visits. Specifically, rescue medication data, E-RS/EXACT-PRO, e-diary data windowing conventions will be up to Week 24 whilst COPD exacerbation will be up to Week 48.
- - For patients who completed the study or who discontinue study medication but continue in the study:
- Week 24 subset:
 - Week 1 = Actual study Day of Week 24 visit minus 168 days (inclusive) up to and including actual study day of week 24 visit minus 161 days
 - Week 2 = Actual study Day of Week 24 visit minus 161 days up to and including actual study day of week 24 visit minus 154 days

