17.1. ADVERSE EVENTS

Adverse Events (AEs) will be coded using MedDRA central coding dictionary. The version of MedDRA to be used will be specified prior to database lock.

Treatment-emergent adverse events (TEAEs) are defined as AEs that started or worsened in severity on or after the first dose of study medication. Laboratory or ECG findings from procedures or samples drawn prior to the first does of study medication that are assessed/overread after randomization will be considered pre-treatment.

In the case where it is not possible to define an AE as treatment-emergent or not, the AE will be classified by the worst case; i.e. treatment-emergent.

See Appendix 2 for handling of partial dates for AEs.

An overall summary of number of patients within each of the categories described in the sub-section below, will be provided as specified in the shells. The summary AE tables will be presented for overall (up to the end of study for all patients) and separately for data up to week 24 visit (regardless of which treatment duration stratum a patient is randomized into) and data from week 24 up to week 48 visit.

In addition, the number of patients with each of the following AE events will be presented by SOC and PT and summarized by treatment group and different period (i.e. Treatment period (+3

[REDACTED]	[REDACTED]	[REDACTED]	[REDACTED]
[REDACTED]	[REDACTED]	[REDACTED]	[REDACTED]
[REDACTED]	[REDACTED]	[REDACTED]	[REDACTED]
[REDACTED]	[REDACTED]	[REDACTED]	[REDACTED]

days), Follow-up (last dose + 4 days) and Overall). These will also be presented for overall, up to week 24 visit, and from week 24 up to week 48 visit:

- TEAE
- TEAEs causally related to study medication
- Serious TEAEs
- TEAEs with an outcome of death
- TEAEs leading to discontinuation of blinded study medication
- TEAEs leading to withdrawal from study (TEAEs with a diagnosis of COVID-19, TEAEs with no diagnosis of COVID-19)
- TEAEs by maximum severity (Mild, Moderate, Severe)

AEs will be identified by using the “Adverse Events” page of the eCRF. Listings will include TEAEs and Non-TEAEs.

Treatment period is defined as the period from the date and time of first dose up to the last date and time of last dose.

Follow-up is defined as the period from after the date and time of last dose up to the last date recorded on the study.

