17.2. LABORATORY EVALUATIONS

Results from the central laboratory (or local laboratory where this is required) will be included in the reporting of this study for chemistry, hematology and viral serology. A list of laboratory assessments to be included in the outputs is included in the Appendix 3 of the study protocol. The handling of Russian laboratories is detailed in Section 6.10 of the SAP.

Presentations of all laboratory tests will use either conventional or standard international (SI) units. However, certain laboratory tests will also be presenting using US units, including liver tests. Laboratory evaluations will be presented separately for 24-week and 48-week strata.

The handling of re-test and unscheduled measurements is detailed in Section 6.4 of the SAP.

The following summaries will be provided for chemistry and hematology data:

- Actual and change from baseline by visit (for quantitative measurements)
- Incidence of abnormal values according to normal range criteria
- Shift from baseline according to normal range criteria (for quantitative measurements and categorical measurements)
- Shift from baseline according to markedly abnormal criteria (for quantitative measurements and categorical measurements)
- Listing of patients meeting markedly abnormal criteria

Viral serology, COVID-19 sample, chemistry and hematology will be listed. The original reference ranges recorded by the local sites or provided by InVitro used for chemistry and hematology parameters will be included in the listing.

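### After Week 24 the all-patients weekly exacerbation percentages keep finished 24-week patients in the denominator, which builds in a ratio of about 1.8 against ensifentrine (minor, descriptive display only)

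*SAP*

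**What the plan says.** SAP section 16.3.3 sets three cut-off rules for exacerbations. The first is "All patients (patients in 24-week and 48-week strata combined) using full study length"; the others truncate at the Week 24 visit and restrict to the 48-week stratum. Under each rule, "the number of patients who experienced COPD exacerbation will be presented by week, follow-up and overall". The denominators are stated: "For All patients and Period truncated at Week 24 visit, the percentage will have denominator of mITT population", and "Analysis using 48-week stratum only will have mITT patients in this stratum as denominator". Nothing reduces the first denominator after Week 24.

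Section 6.4 confirms that the weekly display extends past Week 24: "e-diary data windowing conventions will be up to Week 24 whilst COPD exacerbation will be up to Week 48". Its windows for 24-week patients stop at Week 24. Protocol section 1.3, footnote 19, reserves the Week 30 to Week 48 procedures for the 48-week subset.

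For adverse events, section 17.1 reads: "summary AE tables will be presented for overall (up to the end of study for all patients) and separately for data up to week 24". A third set of tables covers Week 24 to Week 48. The overall tables pool both strata. Elsewhere the SAP keeps the strata apart: "Laboratory evaluations will be presented separately for 24-week and 48-week strata". Sections 17.3 and 17.4 do the same for ECG and vital signs, and section 16.3.3 truncates healthcare resource use at Week 24 or limits it to the 48-week stratum.

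**The concern.** In Weeks 25-48 a patient from the 24-week stratum can no longer enter the numerator of the all-patients percentage but still counts in its denominator. That would dilute both arms equally if the strata had the same allocation ratio. They do not: the 48-week stratum is randomized 3:1 and the 24-week stratum 1:1. The placebo percentages are therefore diluted more, and the late weeks show an apparent excess on ensifentrine that comes from the design.

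What is at stake is how one descriptive display reads. It would understate the sponsor's own product, and its late weeks would disagree with the 48-week-stratum display in the same report.

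The overall adverse event percentages share the cause in weaker form, because the ensifentrine arm is observed longer on average. Safety data have no planned between-group comparison (SAP section 17), so these percentages will be compared by eye.

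**Working it through.** **Inputs** (Protocol section 1.1): 48-week subset about 400 patients, 3:1; 24-week subset about 400, 1:1; arm totals 500 and 300.

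**The plan's own totals.** Ensifentrine: 400 × 3/4 + 400 × 1/2 = 300 + 200 = 500. Placebo: 400 × 1/4 + 400 × 1/2 = 100 + 200 = 300. Both agree with the protocol.

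**Weekly percentage after Week 24, no drug effect.** Let r be the weekly risk and d the dropout common to both arms.

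- Ensifentrine: 300(1 − d)r / 500
- Placebo: 100(1 − d)r / 300
- Ratio: (300/500) / (100/300) = 0.600 / 0.333 = 1.80, whatever r and d are.

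For example, an assumed r of 1% with no dropout shows 3/500 = 0.60% against 1/300 = 0.33%. With a true risk ratio RR, the expected displayed ratio is 1.8 × RR.

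**Sensitivity to the size of the 48-week subset**, with n in that subset out of 800 and the allocation ratios unchanged:

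- n = 350: 262.5/487.5 = 0.538 and 87.5/312.5 = 0.280, ratio 1.92.
- n = 450: 337.5/512.5 = 0.659 and 112.5/287.5 = 0.391, ratio 1.68.

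**With the denominator corrected.** Dividing by the 48-week-stratum patients still in follow-up gives r in both arms, ratio 1.00. Dividing by the whole 48-week-stratum mITT (300 and 100) also gives 1.00 if dropout is equal. If 80% and 70% are retained on ensifentrine and placebo, that fixed denominator gives 0.80/0.70 = 1.14, hence the preference for patients still in follow-up.

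**Overall adverse event percentages (secondary).** Mean planned follow-up is 0.4 × 24 + 0.6 × 48 = 38.4 weeks on ensifentrine and (2/3) × 24 + (1/3) × 48 = 32.0 weeks on placebo. Assume the same risk in both strata and arms. Let F24 and F48 be the proportions with an observed event by Weeks 24 and 48, and x = F48/F24. With equal dropout the ratio of patient percentages is

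(0.4 + 0.6x) / (2/3 + x/3).

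- If the hazard does not rise, x lies between 1 and 2, so the ratio lies between 1 and 1.6/1.333 = 1.20.
- 24-week risk 10%, constant hazard, no dropout: x = 0.19/0.10 = 1.9, ratio 1.54/1.30 = 1.18.
- 24-week risk 50%, same conditions: x = 1.5, ratio 1.30/1.167 = 1.11.
- Rare event whose hazard doubles after Week 24, no dropout: x = 3, ratio 2.2/1.667 = 1.32.
- Rare event, hazard quartered after Week 24, dropout per 24 weeks 30% on ensifentrine and 20% on placebo. In units of the no-dropout 24-week risk, F24 is 0.30/0.357 = 0.841 and 0.20/0.223 = 0.896, and F48 is 0.841 × 1.175 = 0.988 and 0.896 × 1.20 = 1.076. The arm averages are 0.929 and 0.956, ratio 0.97.

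The documents give no adverse event rate, hazard shape or dropout by arm, so these are illustrations.

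**The case against.** The strongest reply is that the SAP already provides the right display. After Week 24 the 48-week-stratum table has the same numerators over a denominator from that stratum alone. Inference on exacerbations uses log study time as an offset or censors at the end of follow-up, and exacerbations are outside the testing hierarchy. All of that stands and is why the point is minor. It does not correct the all-patients percentages, whose denominator the SAP states explicitly.

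A fixed mITT denominator can also be defended as a descriptive convention: the share of the analysis population with an event that week. Taken that way the number is not miscalculated, but it cannot be compared between arms when different fractions of each arm remain under observation.

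The cells will also be small. At a 1% weekly risk about 3 and 1 patients are expected, and the placebo cell is empty in 0.99^100 = 37% of weeks. So 1.8 is a ratio of expected values, not something to be seen in every row. It also presumes the planned 400/400 split. The protocol says approximately, and the analysed mITT excludes some sites (SAP section 5.5).

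On adverse events, the planned tables to Week 24 and for Week 24 to Week 48 already limit the problem, and section 14 summarizes exposure. That stands too.

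**Conclusion.** The all-patients weekly percentages for Weeks 25-48 are wrong as written for comparing arms. Under the planned allocation, no drug effect and equal dropout, the expected ratio is 1.8 against ensifentrine, or about 1.7 to 1.9 for modest departures from the 400/400 split. The realised figure depends on the analysed mITT. The Week-24-truncated and 48-week-stratum displays do not carry this allocation artefact.

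Three stronger readings are tempting and not supported:

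- **That the exacerbation analysis itself is biased.** The negative binomial and time-to-event analyses allow for differing follow-up.
- **That the overall adverse event percentages are inflated on ensifentrine by a known amount.** With equal dropout and a non-rising hazard the null ratio lies between 1 and about 1.20. A rising hazard can take it higher, and unequal dropout can reverse its direction.
- **That the Week 24 to Week 48 adverse event tables carry the same factor of 1.8.** They would if the whole safety set were the denominator, but the SAP text does not state that denominator, and the table shells, which are not among the documents, may.

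A full set of exposure-adjusted adverse event rates is more than this problem requires.

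**What to change.** In SAP section 16.3.3, state that for weeks after Week 24 in the all-patients display the denominator is the 48-week-stratum mITT patients still in follow-up in that week. Alternatively, end that display's weekly percentages at Week 24 and refer the reader to the 48-week-stratum display. Either is a one-sentence change. The first puts two kinds of denominator in one table, so it needs a footnote; the second avoids that and loses nothing the companion display does not show.

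For the secondary point, split the overall adverse event tables by treatment-duration stratum, as sections 17.2 to 17.4 already do. Planned follow-up is then equal between arms within each table. The cost is extra descriptive output and only about 100 placebo patients in the 48-week tables. Neither change touches trial conduct, data collection or alpha.
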